- j All ICS medications in the 12 months prior to Visit 1 must be recorded in the eCRF along with reason for treatment. To satisfy inclusion criteria #6 and #7, the history of continuous treatment with ICS plus second controller medication for at least 3 months prior to Visit 1 should be documented in source and recorded in the eCRF prior to the date of randomization. All other medications taken for conditions other than asthma in the 3 months prior to Visit 1 must be recorded in the eCRF along with reason for treatment.
- k All total serum IgE, IgA, IgG and IgM results will be redacted from the central laboratory reports except Visit 1, at Visit 3 prior to IP administration and any repeat testing that is performed during the screening/run-in period.
- l FSH test done only in women < 50 years who have been amenorrheic for > 12 months to confirm postmenopausal status.
- m FENO test needs to be completed prior to spirometry. FENO is to be completed at either Visit 2 or Visit 2a.
- n Domiciliary FENO only for those subjects who have opted in at consent. The home FENO device will be dispensed at V2 once all spirometry criteria are met for this visit. If an optional V2a is required, then the home FENO device will be dispensed at this visit once all spirometry criteria are met.
- o dECG to be completed prior to any blood draws.
- p Eosinophils, basophil and monocyte counts will be redacted from the central laboratory reports except Visit 1, at Visit 3 prior to IP administration and any repeat testing that is performed during the screening/run-in period.
- q If Visit 1 is conducted more than 35 days in advance of Visit 3, the Visit 2 and Visit 2a visit window is adjusted to complement the preceding visit date (Visit 1).

Table 2 Schedule of Assessments-Randomization, treatment period (Wk 0 - Wk 52), follow-up (Wk 58 - Wk 64)

	Random-ization	Treatment														EOT Period ^w	IPD ^q	FU	FU	UNS ^v	Details in CSP section or Appendix
Visit	3	4	5	6	7	8	9	10	11	12	13	14	15	16	17		18	19		Details in CSP section or Appendix	
Week	0	2	4	8	12	16	20	24	28	32	36	40	44	48	52		58	64			
Day (visit window)	0	±3	±5	±5	±5	±5	±5	±5	±5	±5	±5	±5	±5	±5	±5		±7	±7			
Procedures																					
Inclusion /exclusion criteria	X																			Section 5.1 and 5.2	
Height ^a															X	X				Section 8.2.2	
Weight								X							X	X				Section 8.2.2	
Health care resource Utilization ^b	X	X	X	X	X	X	X	X	X	X	X	X	X	X	X	X	X	X	X	Section 8.9	

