7.1.1 Procedures for discontinuation of study treatment

Subjects are free to discontinue IP or withdraw from the study at any time without prejudice to further treatment. Discontinuing study treatment is not the same as study withdrawal. Procedures to follow for study withdrawal are detailed below in section 7.3. If the subject decides to withdraw consent, then the reason for this must be recorded separately in the eCRF.

A subject that decides to discontinue IP should always be asked about the reason(s) and the presence of any adverse events. The reason for discontinuing treatment and the date of last IP administration should be recorded in the eCRF. Subjects permanently discontinuing IP administration should be given locally available standard of care therapy, at the discretion of the Investigator. However, treatment with marketed or investigational biologics is not allowed until week 64 even if the subject has discontinued IP. Interaction studies between tezepelumab and other biologics indicated for the treatment of asthma have not been conducted. For additional information regarding pharmacokinetic and pharmacodynamic effects of tezepelumab reference should be made to the investigator brochure.

All subjects who prematurely discontinue IP should return to the study center and complete the procedures described for the premature IP Discontinuation visit (IPD) at 4 weeks (+/-5 days) post last IP administration. Subjects who discontinue treatment should be encouraged to return for all regularly scheduled visits for safety and efficacy assessments.

At the IPD visit the subject will be given three options as to how they will be followed as follows:

1. The subject should be encouraged to return for all regular clinic visits and perform all scheduled assessments until he/she completes a total of 52 weeks treatment period.
2. The subject will be offered follow-up on a monthly basis via telephone calls while continuing diary and ePEF completion (no further procedures will be performed), until the subject completes 52 weeks in the study. In addition to the PRO assessments that are performed at home, the subject may also complete the other clinic specified PRO assessments (as defined in the SoA) at home as well. The subject should return for a follow-up visit 16 weeks (+/- 5 days) (refer to SoA, V19 – Week 64) post last IP administration and for the EOT visit at Week 52 (+/-5 days).

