3. If the subject cannot or does not wish to comply with any of the options above, (or any component of them such as only telephone based visits without completion of the diary and ePEF), they will complete a follow-up visit at 16 weeks (+/-5 days) (refer to SoA, Visit 19 – week 64) post last IP administration. After this visit the Investigator

will only contact the subject at 52 weeks post-randomization. No other study assessments will be performed prior to this contact.

If the last IP administration was after week 36 for options 1 or 2, the subject will return to the clinic for an EOT visit at Week 52 (+/- 5 days), and for option 3, the investigator will contact the subject at 52 weeks post randomization. The subject for options 1, 2 and 3 will then return for a follow-up visit 16 weeks (+/- 5 days) post last IP administration (refer to SoA, V19 – Week 64).

The EOT visit will be completed immediately in the case of subsequent early withdrawal from option 1 or 2. Subjects who do not wish to have any follow-up contacts will be discontinued from the study. All discontinued subjects must return the diary and ePEF devices at the EOT visit.

If the subject chooses option 1, all assessments will be completed as per the SoA as indicated in Section 1.1. If the subject chooses 2 or 3, the key information to be collected during the telephone calls are AEs/SAEs, changes in concomitant medication, health care utilization, and asthma exacerbation information.

Subjects who initially choose options 1 or 2 and subsequently cannot or do not wish to comply with the requirements of their option can continue with a less intensive option (i.e. subject initially choosing option 1 can continue with options 2 or 3, subjects initially choosing option 2 can continue with option 3).

If a subject discontinues IP due to a study specific discontinuation criterion, this should always be recorded as 'Development of study specific discontinuation criteria' on the Discontinuation of Investigational Product form in the eCRF.

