The study will consist of a screening/run in period between 5-6 weeks, a planned treatment period of 52 weeks and a post-treatment follow-up period of 12 weeks. The follow-up period may not apply to subjects who participate in the extension study. Any data collected after a subject is enrolled in the extension study will not be included in the analyses described in this SAP.

During the planned treatment period, investigational product (IP) will be administered Q4W starting at the randomisation visit (Week 0; Day 1), with the last administration occurring at Week 48. IP will not be administered at Week 52. Subjects who prematurely discontinue IP will be encouraged to remain in the study and undergo appropriate study visits/procedures for the full planned 52-week treatment period, despite no longer receiving treatment. At the IP Discontinuation (IPD) visit, the subject will be given the following 3 options (further details are given in the CSP Section 7.1.1):

1. The subject should be encouraged to return for all regular clinic visits and perform all scheduled assessments until he/she completes a total of 52 weeks in the study (the planned treatment period)
2. The subject will be offered follow-up on a monthly basis via telephone calls while continuing eDiary and PEF completion (no further procedures will be performed), until the subject completes 52 weeks in the study
3. If the subject cannot or does not wish to comply with either of the options above (or any component of them, such as only telephone-based visits without completion of the eDiary and PEF), then the investigator will only contact the subject at 52 weeks post-randomisation. No study assessments will be performed prior to this contact.

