2.1.5 Definition of on-treatment

Efficacy analyses

Any efficacy assessment date which occurs between the date of randomisation and minimum (date of last dose of IP + 33 days, date of death, date of study withdrawal) will be considered on-treatment. In particular, this allows a subject who completes treatment according to the protocol to have their Week 52 data included as on-treatment, provided Week 52 is within the protocol visit window after the last dose of IP at Week 48.

Safety analyses

Safety analyses will be presented for subjects in the safety analysis set, which is described further in [Section 2.1.2](#).

For this purpose, any adverse event start date, or any safety assessment date (e.g. laboratory, vital signs), which occurs between the date of first dose of IP and minimum (date of last dose of IP + 33 days, date of death, date of study withdrawal) will be considered on-treatment. In particular, this allows inclusion of any safety-related information which may be reported at or generated from the IPD visit to be considered as on-treatment, provided the IPD visit is within the protocol visit window after premature discontinuation of IP.

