4.2.5.3 Supplementary analyses

The MAR analyses specified in [Section 4.2.5.1](#) will be repeated using on-treatment data only, where the definition of on-treatment is given in [Section 2.1.5](#).

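### The last-dose-plus-33-days cut-off can class a fully dosed completer's in-window Week 52 visit as off-treatment in the supplementary analyses (low severity)

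*SAP*

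**What the plan says.** SAP 2.1.5 counts an efficacy assessment as on-treatment if it falls between randomisation and the "minimum (date of last dose of IP + 33 days, date of death, date of study withdrawal) will be considered on-treatment". The safety definition has the same end point but starts at first dose. The SAP then gives the purpose of the rule: "this allows a subject who completes treatment according to the protocol to have their Week 52 data included as on-treatment". The same sentence ends by attaching a condition to that statement: "provided Week 52 is within the protocol visit window after the last dose of IP at Week 48".

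Dosing is every 4 weeks, "with the last administration occurring at Week 48". In Protocol Table 2 (section 1.1), the row beginning "Day (visit window" allows ±5 days at Week 48 and ±5 days at Week 52, each around its own study week. Protocol 6.2 has a postponed dose given at a visit rescheduled within the allowed window, so a Week 48 dose anywhere in that window is compliant.

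The cut-off is used in the supplementary analyses of the primary endpoint (SAP 4.2.4.3) and of the key secondary endpoints (SAP 4.2.5.3), where the main model "will be repeated using on-treatment data only". It is also written out separately for concomitant medication (3.1.6), extent of exposure (3.3.1) and adverse events (3.3.2).

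**The concern.** The 33 days equal one dosing interval plus one 5-day window. That is enough if the Week 52 window is counted from the last dose. It is not enough if both visits have their own window around the study week, because an early Week 48 and a late Week 52 add up.

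A subject who took every dose and attended both visits in window can then have Visit 17 flagged as off-treatment. The values at risk are those dated at that visit: pre-BD FEV1, AQLQ(S)+12 and ACQ-6 at Week 52, the time point of the key secondary estimates. In the schedule of activities the preceding pre-BD spirometry and AQLQ(S)+12 are at Week 36, so for an affected subject the on-treatment MMRM would have nothing later than Week 36 for those two endpoints.

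On the safety side, an adverse event starting 34 to 38 days after the last dose but before an in-window Visit 17 would leave the on-treatment summaries. It would also leave the exposure-adjusted summaries, which SAP 4.2.8.1 produces for the on-treatment period only.

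**Working it through.** **Inputs** (days after randomisation)
- Week 48 target: 48 × 7 = 336, window ±5, so 331 to 341 (Protocol Table 2).
- Week 52 target: 52 × 7 = 364, window ±5, so 359 to 369 (Protocol Table 2). SAP 3.2.1.1 and 3.2.4.1 also place Week 52 at 364 days with a 5-day allowance.
- Cut-off: last dose + 33 (SAP 2.1.5).

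**The plan's figure.** 28 + 5 = 33. This also matches the IPD visit, which Protocol 7.1.1 times at 4 weeks ±5 days after the last dose (maximum 33). The companion safety sentence in SAP 2.1.5, about the IPD visit, is therefore consistent.

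**Range of in-window gaps**
- Longest: (364 + 5) − (336 − 5) = 369 − 331 = 38 days.
- Shortest: (364 − 5) − (336 + 5) = 359 − 341 = 18 days.

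**When Visit 17 falls after the cut-off.** Let d48 and d52 be the deviations from target, each between −5 and +5. The gap is 28 + d52 − d48. It exceeds 33 when d52 − d48 is 6 or more. Since neither deviation can exceed 5 days, this needs Week 48 at least 1 day early, Week 52 at least 1 day late, and a combined shift of at least 6 days. Gaps of 34, 35, 36, 37 and 38 days arise from 5, 4, 3, 2 and 1 day pairs, which is 15 of 11 × 11 = 121.

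**What happens to the record.** SAP 3.1.5 applies the on/off-treatment flag before visit windowing. The late visit would be at relative day 370 at most (369 + 1), inside the Week 52 window of 351 to 378, but the flag has already removed it. The Week 48 visit, at relative day 332 to 342, cannot fill that window. Week 52 is then missing in the on-treatment analysis unless another on-treatment record falls in days 351 to 378.

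**What is kept**
- The Week 52 ASD mean ends on the morning of day 364. The earliest cut-off after an in-window Week 48 dose is 331 + 33 = 364, so the mean is retained.
- For AAER, an affected subject loses at most 5 of about 364 days at risk (5/364 = 1.4%), and the offset adjusts for it.

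**Size.** The documents give no distribution of visit timing, so the figures below are assumptions: independent deviations, and for the bell-shaped cases normal-density weights on the integers −5 to +5. Completers are taken as 1060 × 0.9 = 954, using the 10% dropout assumption in SAP 1.3.

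| Deviation at each visit | Share affected | Of 954 |
|---|---|---|
| Uniform over the window | 15/121 = 12.4% | 118 |
| SD 3 days | 6.3% | 61 |
| SD 2.5 days | 4.5% | 43 |
| SD 2 days | 2.2% | 21 |
| SD 1.5 days | 0.4% | 4 |
| SD 1 day | under 0.01% | 0 |

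Positive correlation between a subject's two deviations, for example when a delayed schedule carries over, would lower these shares.

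**The case against.** The strongest reply is the proviso. If the window is read as 28 ±5 days from the last dose, 33 days covers it exactly and the SAP sentence is true. SAP 3.3.1 describes the 33 days as an allowance for the dosing interval. SAP 4.2.9.1 restricts Week 52 PK samples to 21 to 35 days after the previous dose, so the plan elsewhere accepts losing Week 52 data by time since dose. Calling data 34 to 38 days after a 4-weekly dose off-treatment is a defensible choice.

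This shows that the sentence is ambiguous rather than plainly false, and a reader who infers the latter goes too far. It does not settle the matter. At 4 weeks, only the IPD visit is timed from the last dose, and the SAP itself counts Week 52 from randomisation. The PK rule also cuts the other way: at 34 or 35 days, 9 of the 15 affected day pairs, the same visit gives a valid PK sample but off-treatment FEV1, AQLQ(S)+12 and ACQ-6. Whatever the sentence means, the rule to be programmed is + 33 days.

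The reply on consequences largely stands. The main analyses follow a treatment policy strategy over the planned treatment period (SAP 4.2.4.1, 4.2.5.1) and keep these data. No on-treatment analysis is in the testing hierarchy. The on-treatment analyses are not the only alternative estimates, since the SAP also has controlled-imputation, tipping-point and COVID-19 analyses. Adverse events after the cut-off remain in the on-study summaries, and laboratory, vital-sign and ECG summaries already use the on-study period. Data missing because of scheduling are a benign case for a likelihood-based MMRM, so the loss is one of precision; nothing in the documents shows bias.

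**Conclusion.** The point holds, at low severity. The 33-day rule does not cover every completer whose Week 48 and Week 52 visits are both in window; gaps of 34 to 38 days fall outside it. The effect is confined to visit-dated Week 52 data and a few days at risk in the supplementary on-treatment efficacy analyses, and to the on-treatment medication, exposure and AE periods.

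Three stronger inferences are not supported:
- That the confirmatory results lose Week 52 data. They use the planned treatment period.
- That any early/late pair is excluded. The shifts must total at least 6 days, and a shift at one visit alone never exceeds 33 days.
- That some minimum number of subjects must be affected. About 0 to 120 of about 950 completers is possible, depending wholly on the assumed spread and independence of visit timing. The day arithmetic itself needs no assumption.

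**What to change.** In SAP 2.1.5, for subjects who received the Week 48 dose and did not prematurely discontinue IP, end the on-treatment period at the later of last dose + 33 days and the date of Visit 17, provided that visit is within Week 52 ±5 days. Death or study withdrawal still ends it earlier. Keep last dose + 33 days for premature discontinuers, where it matches the IPD window.

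Use the same definition in SAP 3.1.6, 3.3.1 and 3.3.2, where the 33 days are written out. Changing 2.1.5 alone would leave the efficacy, medication, exposure and AE periods out of step. If the sponsor prefers the present cut-off, 2.1.5 should at least say that the window meant is 28 ±5 days from the last dose, and that some compliant Week 52 visits will therefore count as off-treatment.

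The cost is a short SAP edit in four places and one derivation change. The downsides are that up to 5 extra days count as on-treatment for some completers, and that completers and discontinuers have different end rules.

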2.2 Violations and deviations

Only important PDs will be listed and tabulated in the CSR, and only for randomised subjects (not screening failures). These are defined as PDs which may significantly affect the completeness, accuracy and/or reliability of the study data, or which may significantly affect a subject's rights, safety or well-being. Important PDs in this trial will be grouped under one of the following categories:

- Did not fulfil key eligibility criteria
- Developed discontinuation criteria but continued IP
- Received prohibited concomitant medication
- Did not comply with restrictions during the study
- Did not adhere to protocol-required procedure
- IP management issues
- GCP violation deviations
- Safety reporting and other safety deviations

All-important PDs will be identified and documented by the study team prior to unblinding of the trial at the primary database lock. As far as possible, the occurrence of important PDs will be monitored (blinded) during the trial, with the emphasis on their future prevention.

With the exception of the PK analyses, important PDs will not be used to exclude any subject from any analysis set, nor to exclude any data from subjects included in an analysis set.

The study PD plan outlines the management of PDs and includes the proposed specific categories of PDs in this trial. Any PDs which are not defined as important will not be reported and discussed in the CSR.

3. PRIMARY AND SECONDARY VARIABLES

3.1 General definitions

3.1.1 Definition of baseline

In general, the last non-missing measurement on or prior to the date of randomisation will serve as the baseline measurement for efficacy variables. If there is no value on or prior to the date of randomisation, then the baseline value will not be imputed, and will be set to missing.

In general, the last non-missing measurement prior to first dose of study treatment will serve as the baseline measurement for safety and pharmacokinetic variables. If there is no value prior to first dose of study treatment, then the baseline value will not be imputed, and will be set to missing.

Where unscheduled/repeat assessments are relevant and exist for any subject at a particular visit they will also be considered in the baseline definitions, provided they remain prior to the date of randomisation (efficacy) or the date of first dose of study treatment (safety).

For weekly mean scores derived from subject eDiary (including, but not limited to, Asthma Symptom Diary score) and weekly means of home-based PEF, baseline is defined as the mean of the available data in the most recent week prior to the date of randomisation. If more than 3 days are missing in this week, then the baseline weekly mean will be missing. The “most recent week” starts with the evening measurement one week prior to date of randomisation and ends with the morning measurement on the day of randomisation.

For daily assessments which are made in both morning and evening, the whole day is defined by the assessments in the evening and the following morning. The daily assessment will be considered missing if either evening or following morning is missing. However, some analyses may consider morning and evening separately.

For home-based FENO, baseline is defined as the mean of the available data in the most recent week prior to the date of randomisation. If more than 3 days are missing in this week, then the baseline weekly mean will be missing. For a subject who receives the first dose as scheduled at the randomisation visit, the “most recent week” starts 7 days prior to date of randomisation and ends 1 day prior to date of randomisation.

Baseline for CGI-C and PGI-C is not applicable by definition of these variables.

For safety variables (vital signs, weight/BMI, haematology, clinical chemistry, urinalysis, 12-lead ECG), baseline will be defined as the latest non-missing assessment prior to first dose. If no time is recorded for an assessment, and the assessment takes place at Visit 3, this will be assumed to be a pre-dose assessment.

3.1.2 Absolute change from baseline

Absolute change from baseline is defined as (*post-baseline value - baseline value*).

If either the post-baseline value or the baseline value is missing, then the absolute change from baseline will also be missing.

Unless otherwise specified, “change from baseline” is assumed to be the absolute change from baseline.

3.1.3 Reversibility

Percentage reversibility is defined as follows, for pre-BD and post-BD measurements taken on the same date:

$$\%Reversibility = [(Post-BD FEV_1 - Pre-BD FEV_1) / Pre-BD FEV_1] \times 100\%$$

The FEV₁ post-BD measurement in the reversibility derivation is the measurement after up to 4 SABA inhalations.

3.1.4 Study periods

The following study periods are defined for analysis purposes:

- Screening/run-in period: starting on the date of the first study procedure and ending one day prior to randomisation (for randomised subjects) or on the date of the last study procedure (for screening failures). If any subject is re-screened, the latest available screening will be used for this purpose.
- Planned treatment period (on-treatment and off-treatment): starting on the date of randomisation (efficacy) / date of first dose of IP (safety) and ending on the date of the Week 52 visit or earlier study withdrawal date (for subjects not followed up until Week 52).
- On-treatment period: starting and ending on the start and end dates defined in [Section 2.1.5](#) for efficacy and safety analyses, respectively.
- Post-treatment period/Follow-up period: starting one day after the end date of the on-treatment period defined in [Section 2.1.5](#) for efficacy and safety analyses, respectively, and ending on the study completion or withdrawal date. Note: for subjects entering the extension study, the study completion date will be the day of enrolment in the extension study.
- On-study period (planned treatment and follow-up): starting on the date of randomisation (efficacy) / date of first dose of IP (safety) and ending on the study completion or withdrawal date. Note: for subjects entering the extension study, the study completion date will be the day of enrolment in the extension study. For analysis performed at primary database lock, the on-study period is understood to include all data recorded up until the date of the data cut-off for the primary

database lock (which includes all follow-up data available at the time of the data cut-off).

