- ^w Subjects completing the EOT period, may be eligible to enroll in a separate extension study D5180C00018 and that these subjects will not complete the follow-up visits at Week 58 and Week 64. During the Corona Virus Disease 2019 (COVID-19) pandemic, subjects enrolling in the separate extension study D5180C00018 will continue participation in the follow-up visit(s) (Week 58, Week 64) until the on-site visit (or alternate site) for extension study randomization and IP administration can be conducted.

EOT End-of-Treatment; FU Follow-up; IPD Investigational Product Discontinuation; UNS Unscheduled; W Week.

CHANGES REQUIRED DURING THE COVID-19 PANDEMIC

Please Note: Changes below should only be implemented during the COVID-19 pandemic.

During the COVID-19 pandemic, changes are being implemented in order to ensure the safety of study subjects, to maintain compliance with good clinical practices, and to minimize risks to data integrity. Where allowable by local health authorities, ethics committees and healthcare provider guidelines (e.g. hospital policies), these changes include:

- The option of home visits including home administration of Investigational Product (IP) performed by a qualified Health Care Professional (HCP). Additional information related to the visit can be obtained remotely by phone call and/or video conference. The rationale for this change is to minimize the risk of subjects missing scheduled IP administration and visit assessments due to inability/unwillingness to visit the site during the COVID-19 pandemic.
- Remote visits (phone call and/or video conference) to replace on-site visits, if subjects cannot attend the visits at the study site,

at an alternate site or have home visits. The rationale for this change is to ensure that assessments and collection of information continue for visits that cannot be done at the site, at an alternate site or at the subject's home. This will reduce the risk of subject exposure to COVID-19

- Subjects aimed to transition to the extension study D5180C00018 to continue participation in the safety follow-up visit(s) (Week 58, Week 64) until the on-site (or alternate site) extension study randomization and IP administration can be conducted. The rationale for this change is to ensure randomization/first IP administration in the extension study D5180C00018 can be performed at the site (or alternate site) and to increase the chances of subjects transitioning to the extension study.

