5. STUDY POPULATION

Prospective approval of protocol deviations to recruitment and enrolment criteria, also known as protocol waivers or exemptions, is not permitted.

Each subject should meet all the inclusion criteria and none of the exclusion criteria for this study in order to be assigned/randomized to a study intervention. Under no circumstances can there be exceptions to this rule. Subjects who do not meet the entry requirements are screen failures (refer to section [5.4](#)).

In this protocol, “enrolled” subjects are defined as those who sign the informed consent. “Randomized” subjects are defined as those who undergo randomization and receive a randomization number.

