9.3 Populations for analyses

For purposes of analysis, the following populations are defined:

Population	Description
Enrolled	All subjects who sign the ICF
Randomly Assigned to Study treatment	All subjects randomized to study treatment (irrespective of whether treatment is subsequently taken)
Full Analysis Set	All subjects randomised to study treatment who received at least one dose of IP, irrespective of their protocol adherence and continued participation in the study.
Safety Analysis Set	All subjects who received at least one dose of IP.

Pharmacokinetic analysis set (PK)	All subjects in the full analysis set who received tezepelumab; including PK blood samples that are assumed not to be affected by factors such as protocol deviations (e.g. disallowed medication or incorrect study medication received).
-----------------------------------	--

For analysis of efficacy variables, subjects will be assigned to the full analysis set (defined above) according to their randomized treatment.

Safety presentations and anti-drug antibodies (ADA) presentations will be based on the safety analysis set, with subjects assigned according to their actual treatment. Further details of how actual treatment will be determined for analysis in the event of treatment dispensing errors etc. will be specified in the SAP. Any important deviations from the randomized treatment assignment, and any subjects that have received investigational product without being randomized, will be listed and considered when interpreting the safety data.

All PK summaries will be based on the PK analysis set.

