2. ANALYSIS SETS

2.1 Definition of analysis sets

All subjects analysis set

This analysis set comprises all enrolled subjects who signed the informed consent form, including screening failures, and will be used for the reporting of disposition.

Randomised subjects analysis set

This analysis set comprises all subjects randomised to study treatment, irrespective of whether IP was subsequently taken, and will also be used for the reporting of disposition.

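### The SAP ends follow-up at an undefined extension enrolment date, which could exclude post-Week 52 safety, PK and ADA data that the protocol collects until extension randomisation

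*SAP*

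**What the plan says.** **The cut-off.** SAP 3.1.4 ends the post-treatment and on-study periods at study completion or withdrawal and adds that "for subjects entering the extension study, the study completion date will be the day of enrolment in the extension study". The same note is repeated for medications (SAP 3.1.6) and adverse events (SAP 3.3.2). SAP 1.2 makes it a general exclusion: "Any data collected after a subject is enrolled in the extension study will not be included in the analyses described in this SAP".

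**The word.** Protocol section 5 says that enrolled "subjects are defined as those who sign the informed consent" and defines randomised subjects separately. Protocol 9.3 describes the Enrolled population as "All subjects who sign the ICF". SAP 2.1 uses the word in the same way for its all-subjects set: "This analysis set comprises all enrolled subjects who signed the informed consent form, including screening failures". All three concern the parent study.

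**The data collected.** In normal conditions, subjects going into the extension have no further visits here: "these subjects will not complete the follow-up visits at Week 58 and Week 64". During the pandemic, protocol Table 2 footnote w changes this. Subjects enrolling in the extension "will continue participation in the follow-up visit(s) (Week 58, Week 64) until the on-site visit (or alternate site) for extension study randomization". Dosing in the extension belongs to that same visit.

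**Text that points the other way.** SAP 3.1.4 also says that, for analyses at primary database lock, the on-study period takes in all follow-up data available at the cut-off. SAP 3.1.5 removes from visit windowing only data that come from the extension study itself.

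**The concern.** The protocol collects up to extension randomisation. The SAP stops counting at extension enrolment. If enrolment means consent, the SAP stops at the earlier of two separate steps, and whatever this study collects between them falls outside the analysis.

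The data at stake are off-drug follow-up after Week 52: adverse events, laboratory, vital signs, ECG, and the Week 64 PK and ADA samples. Protocol 4.1 gives safety and anti-drug antibodies as the purpose of the 12-week follow-up, and the pandemic provision extends those visits to subjects who would otherwise skip them. Losing the Week 64 ADA result can change a subject's classification, because SAP 4.2.9.2 calls a subject persistently positive if the last available post-baseline result is positive. The on-study duration also feeds the study-adjusted adverse event rates in SAP 3.3.2.

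**Working it through.** No power or alpha figure depends on this point. The check compares the texts and then uses study-day arithmetic.

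**Step 1. Reproduce the SAP's target days.** Target day = 7 × week + 1. Week 48 = 337, Week 52 = 365, Week 58 = 407, Week 64 = 449. These match SAP Table 1.

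**Step 2. End of the on-treatment period.** SAP 2.1.5 uses last dose + 33 days (or earlier death or withdrawal). With the last dose at Week 48: 337 + 33 = Day 370. The post-treatment period therefore starts on Day 371. To the Week 64 target it lasts 449 − 370 = 79 days.

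**Step 3. Days excluded.** Let c be the day of extension consent and R the day of extension randomisation. If enrolment is read as consent, the parent-study days excluded up to the Week 64 target are min(R, 449) − c. The documents give neither c nor R. The table assumes values of c and takes R at or after Day 449, so each row is the maximum loss for that c.

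| Assumed consent day c | Days lost to Week 64 target (449 − c) | Post-treatment days kept | Post-treatment days lost |
|---|---|---|---|
| 365 | 84 | 0 | 79 |
| 379 | 70 | 9 | 70 |
| 407 | 42 | 37 | 42 |
| 449 | 0 | 79 | 0 |

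At c = 365 or 379 both follow-up visits at their target days are lost. At c = 407 the Week 58 visit is kept and the Week 64 visit is lost. Whenever R = c the loss is zero.

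**Step 4. Coherence of the periods.** At c = 365 the on-study period ends on Day 365, but the on-treatment period runs to Day 370 because SAP 2.1.5 does not cap it at study completion. Days 366 to 370 (5 days) are then on-treatment but not on-study. The post-treatment period would start on Day 371 and end on Day 365.

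**Step 5. Reach into the efficacy analyses.** SAP 3.1.4 ends the planned treatment period at the Week 52 visit or earlier withdrawal, and the extension note is not attached to that period. SAP 4.2.4.1 and 4.2.5.1 use data up to the end of that period. Protocol 4.1 makes subjects eligible for the extension once they complete planned treatment. The confirmatory analyses therefore do not depend on this cut-off.

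**The case against.** The strongest reply is that enrolment in the extension may simply mean entry into it. Protocol section 5 limits its definition to this protocol, and the other two uses also describe the parent study. The SAP note is worded for subjects entering the extension, and footnote w describes the delayed group as enrolling, so for them the step still lies ahead. On that reading enrolment falls at the delayed extension visit and nothing is lost. The extension protocol is not among the documents, and the text of Appendix I after section I 3 was not available, so nothing is inferred from either. This part stands: it cannot be said that both documents equate extension enrolment with consent. It does not remove the problem, because no other definition is offered and both documents keep enrolled and randomised apart.

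The second reply is that SAP 3.1.4 and 3.1.5 contain text favouring inclusion. That is correct, so the exclusion is not settled. However, the sentence in 3.1.4 covers only analyses at primary lock, while protocol 9.4 plans a final lock after the last Week 64 visit. Neither sentence withdraws the exclusion in SAP 1.2. The result is conflicting rules.

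Three stronger readings are tempting and are not supported:

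- **Loss of Week 52 efficacy data.** This needs extension consent before Visit 17 and a cut-off that applies to the planned treatment period. No text says that the first happens, and the extension note is not attached to that period.
- **Loss of exacerbations from the primary analysis.** SAP 3.2.1.1 already excludes, for every subject, exacerbations starting after the time at risk, which ends no later than Visit 17 for those who attend it.
- **A large affected fraction.** Under assumed uniform accrual from between November 2017 and February 2018, with the last Week 64 visit in Q4 2020, about 20–34% of subjects (0.20 × 1060 = 212 to 0.34 × 1060 = 360) reach Week 52 on or after 11 March 2020. That is only a ceiling. Those affected must also enter the extension, be delayed, and consent before randomisation. None of these proportions is given, and the last could be zero.

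**Conclusion.** The point holds as a defect of definition with a conditional loss of data. The SAP's cut-off is an undefined date. Read with the only meaning the documents give the word, it would discard post-Week 52 safety, PK and ADA follow-up that the protocol deliberately collects under its pandemic provision. It also conflicts with other text in SAP 3.1.4 and 3.1.5.

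For an affected subject the size ranges from 0 days (consent and randomisation on the same day) to 84 days to the Week 64 target (consent on Day 365, extension randomisation not before Day 449). Scheduled visits are lost only for subjects delayed under the pandemic provision. The number of such subjects cannot be derived from the documents. The primary and key secondary analyses, power and alpha are unaffected. The change is worth making because it can only retain data.

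**What to change.** In SAP 1.2, 3.1.4, 3.1.6 and 3.3.2, replace enrolment in the extension study with randomisation in the extension study, which is the point that protocol Table 2 footnote w uses. Add one sentence stating that all data collected under this protocol up to that date are included in the analyses. This brings those sections into line with the existing text on follow-up data at primary lock (SAP 3.1.4) and on visit windows (SAP 3.1.5).

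The cost is wording, plus use of the extension randomisation date in place of the extension enrolment date that the rule already needs. The documents do not say where either date is held, but SAP 4.2.1 already plans to report how many subjects went on to the extension, so some link to that study is foreseen. No new data collection is required. If consent and randomisation always coincide, no result changes.
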